### **3.5.2 Exclusion Criteria**

1. Medical history of Lumason hypersensitivity
2. Hemodynamic instability as defined by rapid escalation of cardiopulmonary support in the past 12-24 hours, as defined by the clinical care team including  $\geq 1$  intensive care physician not part of the study team
3. Pulmonary insufficiency as defined by FiO2 requirements of  $>40\%$  and/or subjects with pulmonary hypertension requiring nitric oxide

In this regard, there is a published report of infusion of the investigational drug in twelve neonates, ranging from 26.9 to 41 weeks gestational age, including four premature infants from 26.9 to 29.5 weeks gestational age [9] as well as 3 additional premature subjects from unpublished data of the sponsor. The infusion of the investigational drug in these neonates and premature infants was safe, and imaging results of good quality.

Subjects who do not meet all of the enrollment criteria may not be enrolled. Subjects will be excluded from the study, if in the judgement of the primary clinical team, they are too unstable to tolerate the procedure.

Any violations of these criteria must be reported in accordance with IRB Policies and Procedures.

## **4 STUDY PROCEDURES**

### **4.1 Screening**

- Identify patients scheduled for abdominal ultrasound for suspected or diagnosed necrotizing enterocolitis
- Review of medical records (for inclusion and exclusion criteria)
- Discussion of the case with neonatologists and study team to determine eligibility
- If subject is considered eligible, written or electronic consent can be obtained at this stage by PI, co-investigator, or neonatologist co-investigator
- Coordinate abdominal ultrasound schedule

### **4.2 Study Treatment Phase**

Subjects enrolled to this clinical trial are anticipated to receive the study drug and have CEUS imaging conducted in the ICU setting. In this case, the study drug and US imaging unit will be brought to the ICU for study drug administration and imaging. Any clinically indicated imaging must be performed prior to contrast-enhanced abdominal ultrasound so as not to delay clinical care.

#### Pre-injection documentation

Prior to injection, vital signs and baseline assessment will be recorded and documented from the medical record and clinically in-place monitoring. Baseline assessment will consist on neurological status as described in the clinical evaluations recorded in the medical chart prior to intervention.

#### Pre-injection evaluation

The exam will include a pre-contrast injection evaluation with FDA-approved technologies (e.g. gray-scale ultrasound, Doppler ultrasound, microvascular imaging) to assess anatomical structures and guide contrast evaluation. This will last approximately 5 minutes.

#### CEUS scan

CEUS duration is of approximately 20 minutes. The CEUS examination will be terminated if there is a deterioration in the subject's clinical status during imaging.

#### 60-minute monitoring period

The study team, who are composed of personnel trained in recognizing signs of infusion reaction, will conduct the 60-minute monitoring period and record any untoward reaction that may be related to the infusion of the contrast drug. The 60 minute monitoring post-CEUS will be conducted by study team members.

Vital signs will be recorded and documented from the medical record and clinically in-place monitoring at 1) 30 minutes post-scanning, and 2) 60 minutes post-scanning. During monitoring, subjects will be assessed for rash, allergic reactions, anaphylaxis, and abrupt deviations from the subject's baseline hemodynamic parameters trend not related to medical intervention.

#### Adverse event assessment and documentation

Adverse events will be recorded at 1) 60 minutes post-scanning when the monitoring period is completed, and 2) through 48 hours post-scanning, with documentation at 48 hours post-scanning if no adverse event presents until this point. During the 48-hour AE assessment period, the following AEs of special interest will also be assessed:

- a. worsening cardiopulmonary status,
- b. worsening pulmonary hypertension, which may be suggested by new requirement of nitric oxide use, elevated pulmonary artery pressures on echocardiography, or differential limb pulse oximetry measurements,
- c. worsening neurological status, and
- d. serious gastrointestinal complications

#### 4.2.1 CEUS #1

- Obtain consent prior to scheduled CEUS exam (if not previously obtained by, PI, co-investigator, or neonatologist co-investigator)
- Record vital signs and baseline assessment prior to injection of contrast
- Perform pre-contrast injection evaluation.
- CEUS scan performed, at the time of suspected or diagnosed necrotizing enterocolitis
- Monitor patients for 60 minutes following the CEUS scan for documentation and treatment of potential adverse events
- Documentation of any adverse events through 48 hours post-scanning

Subjects may undergo surgery as part of clinical care. A second CEUS may be performed at the time of surgery for subjects undergoing surgery as part of clinical care, or at short-term follow-up of clinical condition (approximately within 1-2 weeks after the first scan) for a total of two CEUS exams of 1 hour and 20-minute duration each.

#### 4.2.2 CEUS #2

- Record vital signs and baseline assessment prior to injection of contrast
- Perform pre-contrast injection evaluation.
- CEUS scan performed at the time of surgery for subjects undergoing surgery as part of clinical care, or at short-term follow-up of clinical condition (approximately within 1-2 weeks from the first scan)
- Monitor patients for 60 minutes following the scan for documentation and treatment of potential adverse events
- Documentation of any adverse events through 48 hours post-scanning

Study participation will be complete when the 60-minute monitoring period of the last CEUS performed is complete (after the first CEUS in patients who undergo one exam or after the second CEUS is complete in patients who undergo two exams).

The study team will not use sedation or general anesthesia to conduct the research CEUS scans.

The results of the CEUS imaging will be collected for research purposes only. The results of the CEUS will not be used to direct clinical care decisions, without confirmation of diagnosis by another medically established diagnostic product or procedure.

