Glycerol), Sodium Salt (0.19 mg in 1 mg). Inactive ingredients include Polyethylene Glycol 4000 (strength 24.56 mg in 1 mg) and Palmitic Acid (0.04 mg in 1 mg). The Sulfur hexafluoride lipid microspheres are composed of SF6 (molecular weight 145.9) gas in the core surrounded by an outer shell monolayer of phospholipids consisting of 1,2-Distearoyl-sn-glycero-3-phosphocholine (DSPC) and 1,2-Dipalmitoyl-sn-glycero-3-phosphoglycerol, sodium salt (DPPG-Na) with palmitic acid as stabilizer. Sulfur hexafluoride lipid-type A microspheres fall under Category B, that is, animal reproduction studies have failed to demonstrate a risk to the fetus and there are no adequate and well-controlled studies in pregnant women. 1,2-Distearoyl-sn-glycero-3-phosphocholine (DSPC), with empirical formula C44H88NO8P, has a molecular weight of 790.6. 1,2-Dipalmitoyl-sn-glycero-3-phospho-rac-glycerol sodium (DPPG-Na), with empirical formula C38H74 NaO10P, has a molecular weight of 745.

---

Study Design	Single site, open-label clinical study.
Subject Population	Inclusion Criteria
key criteria for Inclusion and Exclusion:	
 
1. Males and females aged 1.5 years or younger
 
2. Post menstrual age of 29 weeks or older
 
3. Patients with suspected or diagnosed necrotizing enterocolitis
 
4. Patient in the CHOP NICU or PICU
 
5. Parental permission
 

	Exclusion Criteria
	
 
1. Medical history of Lumason hypersensitivity
 
2. Hemodynamic instability as defined by rapid escalation of cardiopulmonary support in the past 12-24 hours, as defined by the clinical care team including <math>\geq 1</math> intensive care physician not part of the study team
 

---

---

3. Pulmonary insufficiency as defined by FiO2 requirements of >40% and/or subjects with pulmonary hypertension requiring nitric oxide

---

**Number Of Subjects** 200; CHOP will be the only site of the study.

---

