#### **3.1.1 Screening Phase**

Potential subjects will be identified by: 1) Identification by neonatologists of patients requiring abdominal ultrasound during the neonatal or pediatric intensive care unit stay for suspected, at risk of or diagnosed necrotizing enterocolitis.

Before discussing participation in the study, we will confirm eligibility by reviewing the subjects' medical records. Participation will be discussed between the PI and the referring neonatologist. Participation will be discussed with the parents/guardian by the neonatologist and/or radiologist after identification and confirmation of eligibility. Consent of the parents/guardian will be obtained prior to the exam by the PI, co-investigator, or neonatologist co-investigator in a private setting. Questions will be answered by the PI, co-investigator, or referring neonatologist co-investigator.

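### The current-state exclusions (support escalation, FiO2 above 40%, nitric oxide) are checked at screening and not re-applied before the CEUS #2 injections; the clear gap is exclusion 3 and the look-back in exclusion 2

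*Combined protocol and SAP*

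**What the plan says.** Two of the three listed exclusions in section 3.5.2 and the synopsis depend on the infant's state at the time.

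- Exclusion 2 is hemodynamic instability, meaning "rapid escalation of cardiopulmonary support in the past 12-24 hours, as defined by the clinical care team including" at least one intensive care physician from outside the study team.
- Exclusion 3 is "Pulmonary insufficiency as defined by FiO2 requirements of >40% and/or subjects with pulmonary hypertension requiring nitric oxide".

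The protocol places the check at the start. Section 3.1.1 says "Before discussing participation in the study, we will confirm eligibility by reviewing" the chart. Section 4.1 lists chart review against the criteria and "Discussion of the case with neonatologists and study team to determine eligibility" among the screening steps. Section 3.5.2 states the effect of failing: "Subjects who do not meet all of the enrollment criteria may not be enrolled".

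Section 4.2.2 describes the second exam: "CEUS scan performed at the time of surgery for subjects undergoing surgery as part of clinical care, or at short-term follow-up of clinical condition", the latter at roughly 1-2 weeks. Before injection it asks for vital signs, a baseline assessment and a pre-contrast ultrasound. Section 4.2 takes the vital signs from the chart and the monitors already in place, and describes the baseline assessment as neurological status. Neither section attaches a go/no-go rule. Sections 3.1.2 and 7.2 give two contrast injections per exam.

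Section 3.5.2 adds a broader clause: "Subjects will be excluded from the study, if in the judgement of the primary clinical team, they are too unstable to tolerate the procedure".

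**The concern.** An infant with suspected or diagnosed NEC can be eligible at screening and, by the second scan, need FiO2 above 40%, be on nitric oxide, or have had a sharp rise in support. The criteria would have kept that infant out of the study. Followed as written, the CEUS #2 steps allow two further injections.

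This matters because section 9.4.1 classes the drug risk as a minor increase over minimal, with no prospect of direct benefit. The same section says unstable cardiopulmonary conditions may raise the risk of serious cardiopulmonary reactions. There is also a compliance question. Section 3.5.2 requires violations of the criteria to be reported, but with no stated re-check it is unclear whether an injection at CEUS #2 in such an infant counts as one.

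**Working it through.** The plan gives no figure on this point to reproduce. The check is a comparison of sections plus one piece of timing arithmetic.

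**Step 1: does the screening check carry forward?** Let S be the time of the eligibility check, T the time of injection and L the look-back in exclusion 2 (12 to 24 hours). Screening covers the period from S − L to S. The period that matters at injection runs from T − L to T. The two do not overlap once T − S exceeds L.

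- Longest reading, L = 24 h: no overlap once T − S is more than 24 h.
- Follow-up scan 7 days after CEUS #1: T − S is at least 7 × 24 = 168 h, because screening precedes CEUS #1. The unchecked stretch between the two periods is at least 168 − 24 = 144 h.
- Follow-up scan at 14 days: T − S is at least 336 h, and the unchecked stretch is at least 336 − 24 = 312 h.
- Surgery-time scan: the protocol gives no interval, so the figure is unknown.

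Exclusion 3 has no look-back. It describes the present, so a check at S does not establish the state at any later T.

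**Step 2: does anything else bar the CEUS #2 injections on these grounds?**

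| Safeguard | When it acts | Bars injection for FiO2 above 40% or nitric oxide? |
|---|---|---|
| Primary clinical team's instability clause (3.5.2) | Mandatory, untimed; can be read to cover CEUS #2 | Only if the team also judges the infant unable to tolerate the scan |
| Question to parents about the listed exclusions (9.4.1, Steps Taken to Minimize Risks) | Untimed, not tied to CEUS #2 | It points to the exclusion list, but is a question to parents with no stated consequence |
| Vital signs and baseline from chart and monitors (4.2, 4.2.2) | Before each injection | No; neither item is named and no rule is attached |
| Investigator withdrawal (4.5) | Optional | No |
| Termination on deterioration (4.2, 4.5.1) | During imaging | No; it acts once the exam is under way |
| Temporary stop after any SAE (8.8) | After a serious event, whether or not drug-related | Only if the worsening was serious and known to the team |

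New nitric oxide use is also named in section 4.2, but as a sign of an adverse event of special interest in the 48 hours after a scan. It is not a condition for giving one.

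**Step 3: is CEUS #1 different?** The steps in 4.2.1 state no injection-time check either, and the interval from screening to first scan is not given. By Step 1 the look-back could lapse there too if that interval exceeds 24 hours. Screening is normally closer to the first scan, so the gap is smaller, but the omission is the same.

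**The case against.** The strongest reply is that the treating clinicians already decide. The instability clause is mandatory, belongs to the primary clinical team, and is worded separately from the bar on enrolment. Exclusion 2 has no numeric threshold and rests on the clinical care team's judgement too. Read as continuing through the study, the clause gives nearly the same protection at CEUS #2. That stands for most of exclusion 2. It does not supply the 12-24 hour look-back or the physician from outside the study team. Nor does it replace exclusion 3: an infant on FiO2 of 45% may be judged able to tolerate a scan and still meet that exclusion.

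A second reply is that staff consult the chart and monitors just before injecting, and section 8.1 says adverse events are monitored throughout the study. A reader might infer from the 48-hour recording of adverse events, and from concomitant medications not being recorded, that worsening between scans would go unseen. The documents do not support that. Those provisions govern study data, while eligibility is settled by chart review and discussion with clinicians. What is missing is an instruction to act on the finding, and the share of the interval outside the 48-hour window does not measure that.

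A third reply is that the exclusions are meant to persist. That may be the intent, but the protocol does not say so. If it is, a sentence saying so costs little.

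**Conclusion.** The point holds in limited form and should be fixed. Exclusion 3 is not a stated bar to the CEUS #2 injections. For exclusion 2, the look-back and the outside physician are not carried over. The same injection-time check is missing, with less consequence, from CEUS #1.

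This rests on reading section 3.5.2 as governing entry, which is how it states the effect, and on the CEUS #2 steps being complete as listed.

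A reader might go further and infer that nothing prevents an unstable infant from being injected at CEUS #2, or that the plan exposes infants to a known harm. Neither follows. Several general safeguards exist, one of them mandatory. The caution about unstable patients in section 9.4.1 follows a statement about adults, and the same section reports no serious adverse event in a neonate. The documents do not say how many infants will have a second scan or how many will then meet exclusion 2 or 3, and they do not allow the risk to be sized. This is a patient-safety gap in the protocol; no analysis in section 6 specifically requires CEUS #2.

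**What to change.** Add this step to section 4.2.2, and the same line to 4.2.1:

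> Immediately before the first injection, confirm and document with the clinical care team (including at least one intensive care physician not on the study team) that exclusions 2 and 3 are not met, counting a 24-hour look-back from this injection; if either is met, do not inject and record the reason.

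Twenty-four hours is the conservative reading of the 12-24 hour range. Keep infants who miss CEUS #2 in the CEUS #1 analysis, and report how many missed it and why.

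The cost is a protocol wording change and one short documented confirmation per exam. The real downside is lost second scans, especially surgery-time scans in the sickest infants. Those are the scans closest to the surgical findings that section 6.2 uses as the reference standard, so the CEUS #2 data will come from more stable infants. CEUS #2 is optional under section 3.1, and reporting the reasons keeps that selection visible. At CEUS #1 the cost is small: an infant stopped there is one the enrolment criteria were meant to keep out.

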#### **4.5 Subject Completion/Withdrawal**

Subjects' families may withdraw their child from the study at any time without prejudice to their child's care. A study investigator may withdraw a subject to protect the subject for reasons of safety or for administrative reasons. It will be documented whether or not each subject completes the clinical study. If the investigator becomes aware of any serious, related adverse events after the subject completes or withdraws from the study, the adverse events will be recorded and reported.

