## **8 SAFETY MANAGEMENT**

### **8.1 Clinical Adverse Events**

Clinical adverse events (AEs) will be monitored throughout the study. Subjects enrolled to this clinical trial are anticipated to receive the study drug and have CEUS imaging conducted in the ICU setting. In this case, the study drug and US imaging unit will be brought to the ICU for study drug administration and imaging. CEUS has a duration of approximately 20 minutes. The 60 minute monitoring post-CEUS will be conducted by the study team members. The study team, who are composed of personnel trained in recognizing signs of infusion reaction (rash, allergic reactions, anaphylaxis) will conduct the 60 minute monitoring period and record any untoward reaction that may be related to the infusion of the contrast drug. Adverse events will be recorded at 1) 60 minutes post-scanning when the monitoring period is completed, and 2) through 48 hours post-scanning, with documentation at 48 hours post-scanning if no adverse event presents until this point. All adverse events suspected of being related to study drug infusion will be reported to the regulatory authorities.

In addition to assessing each patient after dosing, after 10 subjects, a complete safety analysis to determine the safety of continuing the study will be performed.

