## **8.8 Study Stopping Rules**

The study will be stopped for image futility, if non-diagnostic imaging is obtained in the first 3 subjects.

There are some circumstances which potentially may arise, requiring temporary study stop. The FDA requires that the study be stopped for all patients (to allow for review of the protocol and procedures based on study related events) after one episode of anaphylaxis or death or other serious adverse event, regardless of relation to study drug. Therefore, anaphylaxis or death or another SAE will prompt a temporary stop to formally discuss the event with the FDA. As such an event (if deemed unrelated) may not meet the prompt reporting criteria for the IRB, the IRB will be notified as applicable (in accordance with CHOP IRB SOP 408). The study will proceed only with documented concurrence of the FDA (and the IRB, as applicable).

The occurrence of two non-fatal SAEs directly related to use of the study drug or one death directly attributed to use of the study drug will stop the study.

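### Does the plan leave the adverse-event period between the two scans so unsettled that the safety summary or the any-SAE stop cannot be applied?

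*Combined protocol and SAP*

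**What the plan says.** Three parts of the protocol bear on the period.

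- **End of participation.** Section 4.2.2 says "Study participation will be complete when the 60-minute monitoring period of the last CEUS performed is complete", and explains the last scan as "after the first CEUS in patients who undergo one exam or after the second CEUS is complete in patients who undergo two exams". The Synopsis (Study Duration) and 3.3 say the same. The second scan is optional: "A second CEUS may be performed at the time of surgery for subjects undergoing surgery as part of clinical care", or at short-term follow-up, "approximately within 1-2 weeks after the first scan" (4.2.1).
- **Adverse-event recording.** Section 8.1 begins "Clinical adverse events (AEs) will be monitored throughout the study". Later in the same paragraph, recording takes place at 60 minutes and then "through 48 hours post-scanning, with documentation at 48 hours post-scanning if no adverse event presents until this point".
- **Serious events.** Section 8.8 attributes to the FDA a requirement to stop the study for all patients "after one episode of anaphylaxis or death or other serious adverse event, regardless of relation to study drug". Section 4.5 deals with the time after completion: "If the investigator becomes aware of any serious, related adverse events after the subject completes or withdraws from the study", they are to be recorded and reported.

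**The concern.** Take an infant on day 5 after a first scan. If a second scan follows on day 6, the infant was on study on day 5. If the infant dies on day 5, the first scan becomes the last one performed, and participation had ended an hour after it. The outcome itself would then decide whether the infant was under observation.

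If events were counted for as long as an infant is on study, two-exam infants would contribute much more time than one-exam infants, and deaths before a second scan could drop out of the summary. The stop in 8.8 is triggered by a single event whatever its cause and states no period, whereas 4.5 mentions only serious events that are related. An unrelated death between hour 48 and a second scan might therefore halt the whole study on one reading and not on another.

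**Working it through.** **Size of the interval.** Inputs: a 48-hour window after each scan (4.2.1, 4.2.2) and a second scan at about 7 to 14 days (4.2.1).

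| | 7 days | 14 days |
|---|---|---|
| Hours between scans | 7 × 24 = 168 | 14 × 24 = 336 |
| Outside first window | 168 − 48 = 120 | 336 − 48 = 288 |
| Share of interval | 120/168 = 71% | 288/336 = 86% |
| Two-exam infant, 48-hour rule | 48 + 48 = 96 | 96 |
| Two-exam infant, study-long counting | 168 + 48 = 216 | 336 + 48 = 384 |
| Ratio | 216/96 = 2.25 | 384/96 = 4.0 |

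If the second scan, for example at surgery, comes within 48 hours, there is no gap. The ratios matter only if the study-long reading is the one the plan adopts.

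**Which reading the plan adopts.** The 48-hour rule stands in:

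1. 4.2, under adverse event assessment and documentation, where it is treated as a named assessment period;
2. 4.2.1, for the first scan;
3. 4.2.2, for the second scan;
4. 6.3.2, the safety analysis;
5. 8.1, in the same paragraph as the study-long sentence;
6. 8.3, where the paragraph expressly includes serious events;
7. 9.4.1, under steps to minimize risk.

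Study-long monitoring appears once, as the general opening of 8.1, and that paragraph goes on to say when events are recorded. The specific text explains the general sentence.

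**Does participation status alter recording?** No section ties the 48 hours to being on study. They run from each scan whether or not another follows. The infant who dies on day 5 and the infant rescanned on day 6 have the same 48-hour window after the first scan. The 60-minute completion point is therefore a clerical mismatch with the 48-hour documentation.

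**Does the summary become unequal?** Section 6.3.2 repeats the 48-hour rule and tabulates events by their timing relative to the scan. Analysed that way, time at risk is 48 hours per scan, cut short only by death or by a second scan inside the window. The 2.25- to 4-fold imbalance does not arise.

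**The stop.** Section 8.8 has no time limit, and no other section restricts it to 48 hours. Section 4.5 is narrower, but it adds a duty for events learned of after completion; it does not limit 8.8. Section 8.8 also foresees an event judged unrelated and says how the IRB is then informed.

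**How much the period could matter.** The documents give no SAE rate. As an assumption, let the 14-day any-cause SAE risk per infant be q = 5% to 30%, with constant hazard and one scan each. The chance of at least one trigger in 10 infants over w days is 1 − (1 − q)^(10w/14).

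- w = 2: 1 − 0.95^(20/14) = 7%; 1 − 0.70^(20/14) = 40%.
- w = 14: 1 − 0.95^10 = 40%; 1 − 0.70^10 = 97%.

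The period affects how often a stop would occur, but these are illustrations. The mortality figures in 1.1 cannot replace them: the rise from 30% to 64% is tied to perforation, which affects 12% to 31% of infants with NEC, and no timing is given.

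**The case for a change.** The strongest case for a change rests on 8.8. Its trigger is wider than any scheduled collection: after hour 48 nothing in section 4 directs staff to look for unrelated deaths or SAEs, and 4.5 asks only for serious, related ones. Section 8.6 leaves events outside its expedited classes to the annual report, so an unrelated death on day 5 could be handled at once or months later. That staff in intensive care would know of the death does not tell them whether it counts.

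Part of this stands. Section 8.8 names no period, neither does the SAE definition in 8.4, and the wording of 4.5 is narrower than that of 8.8. The conflict with 8.6 is weaker: 8.6 governs expedited safety reports, while 8.8 is a separate duty to pause and consult the FDA. The argument shows that a detail is unwritten. It does not show that the plan, followed as written, leads to a wrong action or a biased summary.

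**Conclusion.** The concern does not call for a change. Recording and summarizing adverse events, serious ones included, is settled at 48 hours after each scan, and the study-long sentence in 8.1 is a general opening to that rule. The unequal observation time depends on a way of counting that 6.3.2 does not use. The 60-minute completion point loses no events, because the 48-hour documentation is required separately after each scan.

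The residue is that 8.8 states no period for the temporary stop. Read literally it has no time limit, so the study team has a usable instruction for any death or SAE that comes to notice. The stop is described as an FDA requirement, and whether the FDA set a period cannot be seen from these documents; any period is for the sponsor and the FDA to settle. The conclusion assumes that analysts follow 6.3.2 and that 8.8 is applied as worded. The uncovered 120 to 288 hours are real for scans 7 to 14 days apart, but the number of events in them is unknown.
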